10.3.2 Definition of SAE

If an event is not an AE per definition above, then it cannot be an SAE even if serious conditions are met (eg, hospitalization for signs/symptoms of the disease under study, death due to progression of disease).

A SAE is defined as any untoward medical occurrence that, at any dose:

- a) Results in death**
- b) Is life-threatening**

The term “life-threatening” in the definition of “serious” refers to an event in which the participant was at risk of death at the time of the event. It does not refer to an event, which hypothetically might have caused death, if it were more severe.

- c) Requires inpatient hospitalization or prolongation of existing hospitalization**

In general, hospitalization signifies that the participant has been detained (usually involving at least an overnight stay) at the hospital or emergency ward for observation and/or treatment that would not have been appropriate in the physician's office or outpatient setting. Complications that occur during hospitalization are AEs. If a complication prolongs hospitalization or fulfills any other serious criteria, the event is serious. When in doubt as to whether “hospitalization” occurred or was necessary, the AE should be considered serious.

Hospitalization for elective treatment of a pre-existing condition that did not worsen from baseline is not considered an AE.

- d) Results in persistent disability/incapacity**

- The term disability means a substantial disruption of a person's ability to conduct normal life functions.

- This definition is not intended to include experiences of relatively minor medical significance such as uncomplicated headache, nausea, vomiting, diarrhea, influenza, and accidental trauma (eg, sprained ankle) which may interfere with or prevent everyday life functions but do not constitute a substantial disruption.

e) Is a congenital anomaly/birth defect

f) Other situations:

- Medical or scientific judgment should be exercised in deciding whether SAE reporting is appropriate in other situations such as important medical events that may not be immediately life-threatening or result in death or hospitalization but may jeopardize the participant or may require medical or surgical intervention to prevent one of the other outcomes listed in the above definition. These events should usually be considered serious.
- Examples of such events include invasive or malignant cancers, intensive treatment in an emergency room or at home for allergic bronchospasm, blood dyscrasias or convulsions that do not result in hospitalization, or development of drug dependency or drug abuse.

10.3.3 Recording and follow-up of AE and/or SAE

AE and SAE recording

- When an AE/SAE occurs, it is the responsibility of the Investigator to review all documentation (eg, hospital progress notes, laboratory reports, and diagnostics reports) related to the event.
- The Investigator will then record all relevant AE/SAE information in the eCRF.
- It is **not** acceptable for the Investigator to send photocopies of the participant's medical records to the Monitoring Team in lieu of completion of the Sanofi/AE/SAE eCRF page.
- There may be instances when copies of medical records for certain cases are requested by the Sponsor. In this case, all participant identifiers, with the exception of the participant number, will be redacted on the copies of the medical records before submission to the Monitoring Team.
- The Investigator will attempt to establish a diagnosis of the event based on signs, symptoms, and/or other clinical information. Whenever possible, the diagnosis (not the individual signs/symptoms) will be documented as the AE/SAE.

Assessment of intensity

The Investigator will make an assessment of intensity for each AE and SAE reported during the study and assign it to 1 of the following NCI CTCAE v.5.0 categories: Mild; Moderate; Severe.

An event is defined as "serious" when it meets at least 1 of the predefined outcomes as described in the definition of an SAE, NOT when it is rated as severe.

Assessment of causality

- The Investigator is obligated to assess the relationship between study intervention and each occurrence of each AE/SAE.
- A “reasonable possibility” of a relationship conveys that there are facts, evidence, and/or arguments to suggest a causal relationship, rather than that a relationship cannot be ruled out.
- The Investigator will use clinical judgment to determine the relationship.
- Alternative causes, such as underlying disease(s), concomitant therapy, and other risk factors, as well as the temporal relationship of the event to study intervention administration will be considered and investigated.
- The Investigator will also consult the Investigator’s Brochure (IB) and/or Product Information, for marketed products, in his/her assessment.
- For each AE/SAE, the Investigator **must** document in the medical notes that he/she has reviewed the AE/SAE and has provided an assessment of causality.
- There may be situations in which an SAE has occurred, and the Investigator has minimal information to include in the initial report to Sanofi. However, **it is very important that the Investigator always make an assessment of causality for every event before the initial transmission of the SAE data to the Monitoring Team.**
- The Investigator may change his/her opinion of causality in light of follow-up information and send a SAE follow-up report with the updated causality assessment.
- The causality assessment is one of the criteria used when determining regulatory reporting requirements.

Follow-up of AEs and SAEs

- The Investigator is obligated to perform or arrange for the conduct of supplemental measurements and/or evaluations as medically indicated or as requested by the Monitoring Team to elucidate the nature and/or causality of the AE or SAE as fully as possible. This may include additional laboratory tests or investigations, histopathological examinations, or consultation with other health care professionals.
- New or updated information will be recorded in the originally completed CRF.
- The Investigator will submit any updated SAE data to the Sponsor within 24 hours of receipt of the information.

10.3.4 Reporting of SAEs

SAE reporting to Sanofi via an electronic data collection tool

- The primary mechanism for reporting an SAE to the Monitoring Team will be the electronic data collection tool.
- If the electronic system is unavailable, then the site will use the paper SAE data collection tool (see next section) in order to report the event within 24 hours.

- The site will enter the SAE data into the electronic system as soon as it becomes available.
- After the study is completed at a given site, the electronic data collection tool will be taken off-line to prevent the entry of new data or changes to existing data.
- If a site receives a report of a new SAE from a study participant or receives updated data on a previously reported SAE after the electronic data collection tool has been taken off-line, then the site can report this information on a paper SAE form (see next section) or to the Monitoring Team by telephone.
- Contacts for SAE reporting can be found in the Investigator Study File.

SAE reporting to Sanofi via paper CRF

- Facsimile transmission of the SAE paper CRF is the preferred method to transmit this information to the Monitoring Team.
- In rare circumstances and in the absence of facsimile equipment, notification by telephone is acceptable with a copy of the SAE data collection tool sent by overnight mail or courier service.
- Initial notification via telephone does not replace the need for the Investigator to complete and sign the SAE CRF pages within the designated reporting time frames.
- Contacts for SAE reporting can be found in the Investigator Study File.

10.4 APPENDIX 4: RECOMMENDED SUPPORTIVE CARE AND/OR DOSE MODIFICATION GUIDELINES FOR DRUG-RELATED ADVERSE EVENTS

Event	Symptoms severity (Nadir) (NCI CTCAE v5)	Management of IMP dosing (ramucirumab))	Management of IMP dosing (tusamitamab rvtansine)	Supportive care guidelines
Infusion-related reaction	Grade 1-2 Mild-moderate Eg, Grade ≤ 2 nausea, headache, tachycardia, hypotension, rash, shortness of breath.	Interrupt ramucirumab infusion and start appropriate treatment. Reduce infusion rate by 50%	Interrupt tusamitamab rvtansine infusion. tusamitamab rvtansine may be resumed only after patient recovery, at half the previous infusion rate ^a .	Give diphenhydramine 50 mg IV and/or dexamethasone 10 mg IV. ramucirumab label should be followed Dexamethasone can be added as premedication for upcoming cycles for tusamitamab rvtansine
	Grade 3-4 Severe Eg, symptomatic bronchospasm, urticaria lesions covering $>30\%$ BSA, hypotension, angioedema.	Interrupt ramucirumab infusion and prematurely definitively discontinue ramucirumab	Interrupt tusamitamab rvtansine infusion and prematurely discontinue tusamitamab rvtansine and consider infusion delay.	Give diphenhydramine 50 mg IV and/or dexamethasone 10 mg IV and/or epinephrine and any required treatment per investigator judgement.
Ocular toxicity: Keratopathy/keratitis ^b associated with tusamitamab rvtansine	Grade 1 - Asymptomatic Corneal lesions only observed on routine ocular examination and not requiring topical treatment.	Administer ramucirumab at same dose, and same day as tusamitamab rvtansine	Next infusion of tusamitamab rvtansine at the same dose, with or without cycle delay, depending on the recommendation from the ophthalmologist (nature and extent of the lesion).	Standard ocular examination is planned as recommended by the ophthalmologist.
	Grade 2 Symptomatic or requiring topical treatment (curative) or limiting instrumental activity of daily life. Moderate decrease in visual acuity (best corrected visual acuity 20/40 and better or 3 lines or less decreased vision from known baseline)	Administer ramucirumab as planned, and re-introduce tusamitamab rvtansine when recovery to Grade 1	1 st episode: Omit tusamitamab rvtansine until resolution to Grade 1 (asymptomatic) and restart tusamitamab rvtansine at the same dose. 2 nd episode: Omit SAR until resolution to Grade 1 (asymptomatic) and tusamitamab rvtansine dose reduction. 3 rd episode: depending on benefit risk, premature definitive discontinuation of tusamitamab rvtansine may be envisaged	Standard ocular examination weekly until resolution ^{c, d} . Start curative treatment per ophthalmologist recommendation. After resuming study treatment, participant should be followed with standard ocular examination by every 2 cycles, even asymptomatic during next 4 cycles. If no recurrence, standard process with follow-up with ocular symptom is resumed. Management of study drug upon recurrence to be discussed according to Grade of the event at recurrence, clinical benefit from study drug and recommendation from the ophthalmologist.

Event	Symptoms severity (Nadir) (NCI CTCAE v5)	Management of IMP dosing (ramucirumab))	Management of IMP dosing (tusamitamab rvtansine)	Supportive care guidelines
	Grade 3 Symptomatic with marked decrease in visual acuity (best corrected visual acuity worse than 20/40 or more than 3 lines of decreased vision from known baseline, up to 20/200); corneal ulcer; limiting selfcare activity of daily life	Administer ramucirumab as planned, and re-introduce tusamitamab rvtansine when recovery to Grade 1	1 st episode: Omit tusamitamab rvtansine until resolution (asymptomatic) and restart tusamitamab rvtansine with dose reduction. 2 nd episode: definitive discontinuation of tusamitamab rvtansine.	Standard ocular examination weekly until resolution ^{c, d} . Start curative treatment per ophthalmologist recommendation. After resuming study treatment, participant should be followed with standard ocular examination by every 2 cycles, even asymptomatic during next four cycles. If no recurrence, standard process with follow-up with ocular symptom is resumed Management of study drug upon recurrence to be discussed according to Grade of the event at recurrence, clinical benefit from study drug and recommendation from the ophthalmologist
	Grade 4 Perforation or best corrected visual acuity of 20/200 or worse in the affected eye.	Administer ramucirumab as planned,	Definitive discontinuation of tusamitamab rvtansine.	Complete the corneal examination as recommended by ophthalmologist. Repeat the standard ocular examination weekly ^c until resolution ^d . Start curative treatment per ophthalmologist recommendation.
Conduction disorder associated with tusamitamab rvtansine	Grade 1 Mild symptoms	Administer ramucirumab as planned,	tusamitamab rvtansine administration to be continued upon decision by the Investigator and Sponsor, depending on the nature of the conduction disorder.	ECG performed once weekly until event resolution. Additional evaluations such as LVEF and Holter monitoring should be performed when relevant.
	Grade ≥2	Administer ramucirumab as planned,	Definitive discontinuation of tusamitamab rvtansine.	ECG to be repeated twice weekly until event resolution. Prompt cardiology consultation Additional evaluations such LVEF and Holter monitoring should be performed when relevant.

Event	Symptoms severity (Nadir) (NCI CTCAE v5)	Management of IMP dosing (ramucirumab)	Management of IMP dosing (tusamitamab rfvansine)	Supportive care guidelines
Peripheral neuropathy	Grade 1: Asymptomatic	Administer ramucirumab as planned,	Administer tusamitamab rfvansine as planned,	Patient who has ongoing Grade 1 neuropathy has high risk of worsening of his/her symptoms and should be closely followed.
	Grade 2: Moderate symptoms; limiting instrumental Activities of Daily Living	Delay cycle until recovery to ≤ Grade 1; at next cycle, administer ramucirumab as planned,	Delay cycle until recovery to ≤ Grade 1 and dose reduction if no improvement with dose delay	
	Grade 3: Severe symptoms; limiting self care Activities of Daily Living	Administer ramucirumab as planned,	Definitive discontinuation of tusamitamab rfvansine	
	Grade 4: Life-threatening consequences; urgent intervention indicated	Administer ramucirumab as planned,	Definitive discontinuation of tusamitamab rfvansine	
Neutrophil count decreased	Grade 1 <LLN - 1500/mm ³ ; <LLN - 1.5 × 10 ⁹ /L	No change in IMPs administration.	No change in IMPs administration	No intervention.
	Grade 2 <1500 - 1000/mm ³ ; <1.5 - 1.0 × 10 ⁹ /L	Delay the cycle until recovery of absolute neutrophil count >1500/mm ³ . Restart at the same dose.	Delay the cycle until recovery of absolute neutrophil count >1500/mm ³ . Restart at the same dose.	No intervention.
	Grade 3 <1000 - 500/mm ³ ; <1.0 - 0.5 × 10 ⁹ /L Or Grade 4 <500/mm ³ ; <0.5 × 10 ⁹ /L	Delay the cycle until recovery of absolute neutrophil count >1500/mm ³ . Restart when absolute neutrophil count >1500/mm ³ at the same dose. Prophylactic G-CSF should be considered in all subsequent cycles	Delay the cycle. Restart the treatment when absolute neutrophil count >1500/mm ³ at the same dose prophylactic G-CSF can be considered in all subsequent cycles	Follow ASCO guidelines on usage G-CSF and antibiotherapy (20, 23). Repeat test every 3 days.
	Grade 4 >7days <500/mm ³ ; <0.5 × 10 ⁹ /L	Delay the cycle until absolute neutrophil count >1500/mm ³ . 1st episode administer next cycle with ramucirumab at the same dose and administer growth factors 2nd episode: administer ramucirumab as the same dose 3rd episode: definitive discontinuation of IMPs	Delay the cycle until absolute neutrophil count >1500/mm ³ . 1st episode administer tusamitamab rfvansine next cycle at the same dose and administer growth factors 2nd episode: administer tusamitamab rfvansine at reduced dose 3rd episode: definitive discontinuation	Follow ASCO guidelines on G-CSF usage and antibiotherapy. Repeat test every 3 days.

Event	Symptoms severity (Nadir) (NCI CTCAE v5)	Management of IMP dosing (ramucirumab)	Management of IMP dosing (tusamitamab rfvansine)	Supportive care guidelines
Febrile neutropenia	Grade 3 Absolute neutrophil count <1000/mm ³ with a single temperature of >38.3°C (101°F) or a sustained temperature of ≥38°C (100.4°F) for more than 1 hour	Delay cycle until absolute neutrophil count >1500/mm ³ . 1st episode administer next cycle at the same dose and administer G-CSF 2nd episode: administer ramucirumab at reduce dose 3rd episode: definitive discontinuation	Delay cycle until absolute neutrophil count >1500/mm ³ . 1st episode administer next cycle at the same dose and administer G-CSF 2nd episode: administer tusamitamab rfvansine at reduce dose 3rd episode: definitive discontinuation	To ensure relative dose intensity, G-CSF is recommended as secondary prophylaxis in all patients with Grade 3 febrile neutropenia ASCO guideline is recommended for supportive treatment if there are no defined clinical standards (23)
	Grade 4 Life-threatening consequences	Administration changes to be decided at the Investigator's discretion per product label	Administration changes to be decided at the Investigator's discretion. 1st episode: administer next cycle at reduced dose and administer G-CSF 2nd episode: definitive discontinuation	
Hypertension	Grade 3 Severe hypertension	Withhold ramucirumab until controlled with medical management, and restart at same dose	Administer tusamitamab rfvansine as planned	
	Grade 4 Severe hypertension that cannot be controlled with antihypertensive therapy	Definitively discontinue ramucirumab	Administer tusamitamab rfvansine as planned	
Proteinuria	First occurrence of increased urine protein levels greater than or equal to 2 g per 24 hours	Omit ramucirumab until urine protein level is ≤2 g per 24 hours; then resume ramucirumab at a reduced dose (in doublet cohort, 8 mg at 1st episode, then 5 mg if 2nd episode and in triplet cohort, 8 mg at 1 st episode, then 6 mg if 2d episode)	Administer tusamitamab rfvansine as planned	
	Reoccurrence of urine protein level greater than 2 g per 24 hours following initial dose reduction	Omit ramucirumab until protein level is ≤2 g per 24 hours; then resume ramucirumab at a reduced dose:(6 mg or 5 mg)	Administer tusamitamab rfvansine as planned	
	Urine protein level greater than 3 g per 24 hours or in the setting of nephrotic syndrome	Definitively discontinue ramucirumab	Consider benefit/risk for the patient to continue or delay tusamitamab rfvansine infusion	

Event	Symptoms severity (Nadir) (NCI CTCAE v5)	Management of IMP dosing (ramucirumab))	Management of IMP dosing (tusamitamab rvtansine)	Supportive care guidelines
Hemorrhage	Grade 3 or 4	Definitively discontinue ramucirumab	Permanently discontinue tusamitamab rvtansine	
Gastrointestinal Perforation	All Grades	Permanently discontinue ramucirumab	Consider benefit/risk for the patient to continue or delay tusamitamab rvtansine infusion	
Arterial Thromboembolic Events	All Grades	Definitively discontinue ramucirumab	Administer tusamitamab rvtansine as planned	
Wound Healing Complications	All Grades	Definitively discontinue ramucirumab for wound healing complications requiring medical intervention	Consider benefit/risk for the patient to continue or delay tusamitamab rvtansine infusion	

a tusamitamab rvtansine is stable at least 7.5 hours in the infusion bag at room temperature. If necessary, a new infusion should be prepared with the remaining dose to be administered.

b The NCI CTCAE V5.0 grading is to be applied to keratopathy.

c Standard ocular examination per protocol includes visual acuity, slit lamp examination, Schirmer's test, and enquiring for ocular/visual symptoms.

d When possible at the site, photographs should be done when findings are first documented and to follow progression when relevant. Any additional relevant ocular examination can be done if indicated.

Abbreviations: ASCO = American Society of Clinical Oncology, ASOCT = Anterior segment optical coherence, BSA = Body surface area, ECG = Electrocardiogram, G-CSF = Granulocyte colony-stimulating factor, Hb = Hemoglobin, IMP = Investigational medicinal product, IV = Intravenous; LLN = Lower limit of normal, LVEF = Left ventricular ejection fraction, NCI CTCAE = National Cancer Institute Common Terminology Criteria for Adverse Events, RBC = Red blood cell.

Event	Symptoms severity (NCI CTCAE v5.0)	Management of IMP dosing (pembrolizumab)
Infusion-related reactions	Grades 1 or 2	Interrupt or slow the rate of infusion
	Grades 3 or 4	Permanently discontinue
Immune-mediated pneumonitis	Grade 2	Withhold
	Grades 3 or 4 or recurrent Grade 2	Permanently discontinue
Immune-mediated colitis	Grades 2 or 3	Withhold
	Grade 4 or recurrent Grade 3	Permanently discontinue
Immune-mediated hepatitis	AST or ALT greater than 3 but no more than 5 times the ULN or total bilirubin greater than 1.5 but no more than 3 times the ULN	Withhold
Immune-mediated endocrinopathies	Grades 3 or 4	Withhold until clinically stable
Immune-mediated nephritis	Grade 2	Withhold
	Grades 3 or 4	Permanently discontinue
Immune-mediated skin adverse reactions	Grade 3 or suspected Stevens-Johnson Syndrome (SJS) or toxic epidermal necrolysis (TEN)	Withhold
	Grade 4 or confirmed SJS or TEN	Permanently discontinue
Other immune-mediated adverse reactions	Grades 2 or 3 based on the severity and type of reaction	Withhold
	Grade 3 based on the severity and type of reaction or Grade 4	Permanently discontinue
Recurrent immune-mediated adverse reactions	Recurrent Grade 2 pneumonitis	Permanently discontinue
	Recurrent Grades 3 or 4	
Inability to taper corticosteroid	Requirement for 10 mg per day or greater prednisone or equivalent for more than 12 weeks after last dose of pembrolizumab	Permanently discontinue
Persistent Grade 2 or 3 adverse reaction (excluding endocrinopathy)	Grades 2 or 3 adverse reactions lasting 12 weeks or longer after last pembrolizumab	Permanently discontinue

General instructions:

1. Corticosteroid taper should be initiated upon AE improving to Grade 1 or less and continue to taper over at least 4 weeks.
2. For situations where pembrolizumab has been withheld, pembrolizumab can be resumed after AE has been reduced to Grade 1 or 0 and corticosteroid has been tapered.
3. For severe and life-threatening irAEs, IV corticosteroid should be initiated first followed by oral steroid. Other immunosuppressive treatment should be initiated if irAEs cannot be controlled by corticosteroids.

For additional guidelines, please refer to ASCO Guidelines published in 2021 ([24](#)).

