On Day 1 of each treatment cycle, the patient's BSA will be determined using the current weight and baseline height; dose may not be adjusted if body weight change is $\leq 5\%$.

Investigational medicinal products:

Ramucirumab: Ramucirumab should be administered prior to tusamitamab ravtansine infusion. Using a controlled infusion pump, ramucirumab will be administered by IV infusion over 1 hour on D1 of each cycle. If the first infusion is tolerated, all subsequent ramucirumab infusions may be administered over 30 minutes. In case of IRR, Grade 1 or 2, the infusion rate of ramucirumab will be reduced by 50%.

Tusamitamab ravtansine: Infusion of tusamitamab ravtansine should be initiated at least 1 hour after the end of ramucirumab infusion. Using a controlled infusion pump, tusamitamab ravtansine will be administered by IV infusion over 1 hour 30 minutes. For patients with a BSA $>2.20\text{ m}^2$, the calculated dose of tusamitamab ravtansine will be based on a BSA of 2.20 m^2 . After first study intervention of tusamitamab ravtansine, patients should be observed for acute reactions at site up to 4 hours depending on any sign of drug-induced allergic reaction. Detailed instructions for dilution and administration of the IMP is provided in Pharmacy Manual.

Pembrolizumab: Pembrolizumab will be administered after administration of tusamitamab ravtansine in the triplet cohort only. Using a controlled infusion pump, pembrolizumab will be administered as a 200 mg IV infusion over 30 minutes on Day 1 and then Q3W.

Noninvestigational medicinal products:

Premedication:

Both tusamitamab ravtansine and ramucirumab have potential risk of IRR; thus, premedication with an IV histamine-1 receptor antagonist (diphenhydramine 50 mg IV or equivalent; eg, cetirizine, promethazine, dexchlorpheniramine, according to local approval and availability) will be given approximately at least 15 minutes before ramucirumab administration. In case of IV

forms unavailability, a per os administration should be considered in an appropriate timeframe. If a participant previously experienced an IRR following a dose of ramucirumab or tusamitamab ravtansine, premedication will also include corticosteroids equivalent to 10 mg IV dexamethasone, and acetaminophen/paracetamol for future infusions. All drugs used as premedication will be entered on the concomitant premedication page.

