6.6.4 Dose adjustment/dose delay

Dose adjustment and/or cycle delay are permitted in case of adverse reaction. In case of toxicity, cycle delays and dose modifications should be implemented according to Appendix 4 ([Section 10.4](#)). Every effort will be made to administer the full dose regimen and maximize dose intensity.

Dose adjustments will be made according to the worst grade of adverse reaction observed within a cycle. If a participant experiences several adverse reactions and there are conflicting recommendations, the most conservative dose adjustment recommended should be followed.

Administration of the study treatment will be discontinued in the event of a TEAE that persists despite appropriate dose modifications or any other AE that, in the opinion of the Investigator, warrants discontinuation.

Pembrolizumab, ramucirumab or tusamitamab rvtansine can be discontinued prematurely. The patient will remain on study treatment until the last IMP can be discontinued until disease progression, unacceptable AE, or the participant's or investigator's decision to stop the treatment. The reason for premature discontinuation will be captured in the appropriate eCRF page.

Dose modifications different from those stated in the protocol should be made only in consultation with the Sponsor unless required for immediate participant safety.

All changes to study treatment administration must be recorded in the eCRF.

In the event of neutropenia, therapeutic G-CSF should be administered according to the current American Society of Clinical Oncology (ASCO) guidelines ([23](#)). In case of neutropenia or febrile neutropenia, prophylactic G-CSF should be started and in case of second episode beside prophylactic G-CSF, then dose should be reduced.

The acceptable treatment window for tusamitamab rvtansine and ramucirumab and pembrolizumab administration is ± 2 days for a Q2W (doublet cohort) and ± 3 days for a Q3W administration (triplet cohort).

See Appendix 4 in [Section 10.4](#) for further guidance in dose modification or discontinuation. Approved product label should be followed for patient receiving ramucirumab treatment for supportive care and dose modification requirement due to not listed adverse events. During the conduct of the study, second dose reduction may be needed, and need to be decided case by case discussion with the sponsor.

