8.2.6.1 Hypersensitivity reactions

Premedication treatments provided for treatment of hypersensitivity reactions are detailed in [Section 6.1](#).

In case of event of hypersensitivity reactions, please refer to the recommended dose modification or discontinuation table in Appendix 4 ([Section 10.4](#)).

As with other monoclonal antibodies, IRRs may occur during or following ramucirumab or tusamitamab ravidansine or pembrolizumab administration. Patients should be closely monitored for signs and symptoms indicative of an IRR from the initiation of the infusion in an area where resuscitation equipment and other agents (such as epinephrine and corticosteroids) are readily available.

A 1-hour observation period following the ramucirumab infusion is mandatory for the first 2 infusions. If the patient shows no evidence of an IRR with the first 2 infusions of ramucirumab, no observation period is required for subsequent infusions. In the event an IRR occurs thereafter, the 1-hour observation should be reinstated. Symptoms of IRRs include rigors/tremors, back pain/spasms, chest pain and/or tightness, chills, flushing, dyspnea, wheezing, hypoxia, and paresthesia. In severe cases, symptoms include bronchospasm, supraventricular tachycardia, and hypotension. If the patient experiences a Grade 2 IRR, interrupt the infusion and treat the patient with anti-allergic medication. If symptoms resolve, resume the infusion at a reduced rate (50%).

8.2.6.2 *Ocular toxicity*

It is recommended that topical artificial tears (and/or hyaluronic ophthalmic gel) are used regularly in all patients treated with tusamitamab ravidansine during the study treatment period.

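### Appendix 4 tells sites both to discontinue tusamitamab and to consider delaying it after a Grade 3–4 infusion-related reaction; its premedication wording is also weaker than that of Section 6.1

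*Protocol*

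**What the plan says.** **Grade 3–4 reactions (Protocol Section 10.4, Appendix 4).** The tusamitamab cell says: "Interrupt tusamitamab rvtansine infusion and prematurely discontinue tusamitamab rvtansine and consider infusion delay". The ramucirumab cell in the same row says: "Interrupt ramucirumab infusion and prematurely definitively discontinue ramucirumab". The separate pembrolizumab table calls for permanent discontinuation at Grades 3 or 4.

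**Which text governs.** Section 6.6.4 states: "In case of toxicity, cycle delays and dose modifications should be implemented according to Appendix 4". For hypersensitivity reactions, Section 8.2.6.1 tells the site: "please refer to the recommended dose modification or discontinuation table in Appendix 4". Neither section gives its own Grade 3–4 rule for tusamitamab.

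**Premedication after a reaction.** For a participant with an earlier reaction to ramucirumab or tusamitamab, Section 6.1 says: "premedication will also include corticosteroids equivalent to 10 mg IV dexamethasone, and acetaminophen/paracetamol for future infusions". It sets no grade limit, and the synopsis has the same rule in mandatory wording. In Appendix 4, the supportive-care cell of the Grade 1–2 row says: "Dexamethasone can be added as premedication for upcoming cycles for tusamitamab rvtansine". That cell does not mention acetaminophen, and for ramucirumab it defers to the product label.

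**The concern.** The tusamitamab cell gives two actions that cannot both be carried out if discontinuation means stopping the drug. The row covers reactions such as symptomatic bronchospasm and angioedema. What is at stake is whether a participant who has had such a reaction receives the investigational drug again, and two sites following the same table in good faith could act differently.

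The data would differ too. A stop and a delay fall in different rows of the SAP's adverse event tables, so those tables would partly reflect how each site read one sentence.

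The premedication mismatch matters less. Sites relying on different sections could give different premedication after a Grade 1–2 reaction, and that practice feeds the SAP's summary of dexamethasone use and its hypersensitivity event of interest.

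**Working it through.** No sample size, power or error-rate figure is involved, so the check is a comparison of texts. All of them are current text, not amendment history.

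1. **Can the cell be read consistently on its own?** Its first verb already covers stopping the infusion in progress. If discontinuing means stopping the drug, the delay has nothing to act on. If it means only abandoning that day's dose, it largely repeats the first verb, and the cell never says later dosing is allowed. Each reading leaves part of the cell redundant or contradictory.

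2. **Does the protocol's vocabulary settle it?** Not fully. Sections 6.6.4 and 7.1.1 speak of premature discontinuation for stopping one of the drugs, and 7.1.1 does so under a heading about definitive discontinuation. That favors a stop. But where the text wants to be explicit it adds a word: the ramucirumab cell adds *definitively*, Section 6.6.4 has a passage that adds *permanently*, and other tusamitamab cells in Appendix 4 (Grade 4 keratopathy, Grade 2 or higher conduction disorder, Grade 3 or 4 neuropathy) call for definitive discontinuation. The infusion-reaction cell has no such word and adds the delay.

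3. **Does another rule settle it?**
   - Section 6.6.4 says to take the most conservative adjustment, but for several reactions with conflicting recommendations, not for one cell that conflicts with itself.
   - Section 6.6.3 requires drug-related toxicity to have returned to Grade 1 or baseline severity before retreatment. That says when re-dosing may happen in general, not whether it may happen after a Grade 3–4 infusion reaction.
   - Sections 6.6.4 and 8.2.6.1 point back to Appendix 4, so the cross-references end at the unclear cell.

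4. **Where does the event go in the SAP?** Suppose the reaction is to tusamitamab and ramucirumab continues, as Section 6.6.4 permits.
   - Read as a stop: SAP Table 9, permanent partial discontinuation of tusamitamab.
   - Read as a delay: SAP Table 9, dose modification of tusamitamab, which includes delay and omission.
   - The interrupted infusion is counted either way, because SAP Section 4.7.1.2 counts an interruption whether or not the infusion restarts.

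5. **Run-in.** In the doublet, a DLT-evaluable participant needs at least 80% of the intended dose of both drugs at each of the first two infusions, unless a DLT led to discontinuation (Protocol Table 15). Protocol Table 5 lists Grade 4 non-hematologic events as DLTs. A Grade 3 infusion reaction is not listed and would qualify only through the closing catch-all. So for a Grade 3 reaction at the first infusion, not declared a DLT and arising after 80% of the dose had been given, a stop makes the participant non-evaluable and replaced, while a delay with re-dosing could keep the participant evaluable. This route is narrow. In the triplet only one cycle is needed, so a decision about later cycles would not by itself change evaluability.

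6. **Premedication, side by side.**

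| | Synopsis and Section 6.1 | Appendix 4, Grade 1–2 row |
|---|---|---|
| Trigger | Any earlier reaction to either drug, no grade limit | Grade 1–2 reaction |
| Corticosteroid | Required | Optional, stated for tusamitamab |
| Acetaminophen | Required | Not mentioned |
| Ramucirumab | Covered by the same rule | Refers to the product label |

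The overlap is Grade 1–2 reactions. The Grade 3–4 row says nothing on later premedication.

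**The case against.** The best reply on the main point is that the cell plainly means stop, or that any re-dosing would be guarded by the retreatment criteria in Section 6.6.3. The second part stands to this extent: the documents do not support reading the cell as allowing unguarded re-exposure. Neither part decides whether re-exposure is allowed at all.

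On premedication the reply is stronger. Section 8.2.6.1 assigns premedication to Section 6.1 and uses Appendix 4 for dose modification or discontinuation. Appendix 4 describes itself as recommended guidance, and exclusion criterion E26 removes participants who cannot take corticosteroid premedication. A site that follows Section 6.1 breaches neither text. This mostly stands, and leaves a wording mismatch rather than two irreconcilable rules.

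Stronger readings that the documents do not support:

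- **That every reaction is caught by the premedication conflict.** The optional wording is in the Grade 1–2 row only.
- **That Appendix 4 leaves a gap after ramucirumab reactions.** It defers to a label that is not among the documents, so a gap cannot be shown.
- **That the handling of a Grade 1 ramucirumab reaction is contradictory.** Section 6.1 halves the rate for Grade 1 or 2, Appendix 4 interrupts and halves it, and Section 8.2.6.1 says "If the patient experiences a Grade 2 IRR, interrupt the infusion and treat the patient with anti-allergic medication" and then resumes at half rate. All three agree on the 50% rate and none forbids interruption at Grade 1. This is a difference in detail.
- **That the acute treatment instructions conflict.** No such conflict appears.
- **That steroid use on pembrolizumab days is a demonstrated problem in the triplet.** The documents give no basis for this, and the SAP does not cover that cohort.

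**Conclusion.** The main point holds. The Grade 3–4 tusamitamab cell contradicts itself, and no other part of the protocol resolves it. It bears on every Grade 3–4 infusion reaction to tusamitamab, and the choice concerns participant safety.

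The premedication mismatch also holds, as a secondary point confined to Grade 1–2 reactions.

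The size cannot be put as a count. The documents give no infusion-reaction rate for any grade, so any number of participants would merely restate an assumption. The SAP outputs affected are descriptive and record what was done. A reader might infer that the response rate or the DLT result is biased; that is not shown, beyond the narrow evaluability route described above. This is an internal inconsistency to be corrected, not a flaw in the choice of design. The conclusion rests on the wording alone and on no assumed figure.

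**What to change.** 1. The sponsor should reconcile the Grade 3–4 tusamitamab cell into one instruction that states whether any further tusamitamab may be given after such a reaction. It should use discontinuation and delay in the senses of SAP Sections 4.2 and 4.7.1.2, so that each event has one place in SAP Table 9.
2. The synopsis, Section 6.1 and the Grade 1–2 row of Appendix 4 should carry the same premedication statement: required or optional, which medicines, and after a reaction to which drug. A cross-reference from Appendix 4 to Section 6.1 would also serve.

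This review takes no view on which clinical rule is right; that is for the sponsor's clinical team. The cost is wording in two cells of one appendix and, depending on the decision, in the synopsis and Section 6.1. No procedure, data item, sample size or SAP analysis changes. SAP Section 1.1 says the triplet cohort had not started, so correcting the text before its first dose would avoid mixed practice among its 6 to 12 participants.
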